8.0 DRUG INFORMATION

8.1 Cabozantinib

8.1.1 Composition, Formulation, and Storage

At study sites, all study medication will be stored as described in the appropriate prescribing information for that country (if applicable) or the pharmacy manual and inventoried in accordance with applicable state and federal regulations.

8.1.2 Investigational Treatment: Cabozantinib

Cabozantinib tablets are supplied as film coated tablets containing cabozantinib malate equivalent to 20 mg of cabozantinib and contain microcrystalline cellulose, lactose anhydrous, hydroxypropyl cellulose, croscarmellose sodium, colloidal silicon dioxide, magnesium stearate and Opadry® yellow. Doses of 40 mg will comprise two 20-mg tablets. The components of the tablets are listed in Table 0-12.

Table 0-12: Cabozantinib Tablet Components and Composition

Ingredient	Function	% w/w^a
Cabozantinib Drug Substance (25% drug load as free base)	Active Ingredient	31.7
Microcrystalline Cellulose	Filler	38.9
Lactose Anhydrous	Filler	19.4
Hydroxypropyl Cellulose	Binder	3.00
Croscarmellose Sodium	Disintegrant	6.00
Colloidal Silicon Dioxide	Glidant	0.30
Magnesium Stearate	Lubricant	0.75
Opadry® yellow film coating which includes: - HPMC 2910/hypromellose 6 cp - Titanium dioxide - Triacetin - Iron oxide yellow	Film Coating	4.00
^a weight fraction, expressed in percentage; HPMC, hydroxypropyl methylcellulose		

*Refer to the Pharmacy Manual for details on storage and handling of cabozantinib

8.1.3 Availability & Supply

Cabozantinib will be provided in 60 cc HDPE white bottles containing 30 tablets each. Each bottle will be printed with a unique 7-digit bottle number and a lot number for tracking purposes. Please complete the drug order form located in the pharmacy manual. This form includes directions for ordering.

All sites will use Cabozantinib that is provided by Exelixis. Cabozantinib will be shipped directly to lead site (City of Hope) and affiliate sites by Exelixis.

8.1.4 Preparation/Dispensation/Administration

All cabozantinib should be dispensed in the original container supplied by Exelixis and should not be repackaged at any time.

8.1.5 Storage and Stability

Store at controlled room temperature (20-25 degrees Centigrade, or 68-77 degrees Fahrenheit); allowing for excursions between 15 and 30 degrees

Centigrade (59 and 86 Fahrenheit). Please contact Exelixis Clinical Supplies at [contact] immediately in case of any temperature excursions outside the accepted range. All affected IP will need to be quarantined until further notification.

8.1.6 Side Effects

Very common side effects (occurring in $\geq 10\%$ of subjects) of Cabozantinib are: abdominal pain, hypothyroidism, increased liver enzymes, change in voice, diarrhea, constipation, fatigue, mouth sores, hand-foot syndrome, weight loss, decreased appetite, nausea, vomiting, fatigue, oral pain, neutropenia, thrombocytopenia, taste changes, hair color changes, high blood pressure.

Common side effects (occurring in $\geq 1\%$ but $<10\%$ of subjects) are: abnormal thickening of the skin, change in the feeling of touch (paresthesia), cough, bleeding (stomach or intestines, within the brain), blood clots in lungs or legs, confusion and disorientation, anemia, electrolyte imbalance, thrombocytopenia, dehydration, difficulty swallowing, dizziness, dry mouth, dry skin, fever, fungal infections, headache, hemorrhoids, increase in lipase and amylase, muscle spasm, pain and swelling in extremities, protein in urine, shortness of breath, upset stomach or indigestion, stomach acid, ulcer.

Uncommon (occurring in $\geq 0.1\%$ but $<1\%$ of subjects: ventricular arrhythmia, QT prolongation, fistulas, abscesses, blood clot, chest discomfort, cataract, damage to the skeletal muscle tissue, encephalopathy, pancytopenia, destruction of bone tissue, anxiety, gallstones, heart attack, infections, inflammation of the intestine, appendix, gall bladder or thin tissue lining the inner wall of the abdomen, reduced kidney function, liver failure, syncope, pneumonia, rapid heart rhythm, respiratory failure, seizure, stroke, ataxia, throat swelling, temporary paralysis of the intestines.

Please refer to the current Investigator's Brochure (IB) for a complete listing of all toxicities.

8.1.7 Return and Retention of Cabozantinib

The investigator or designee will maintain accurate records of receipt of all study treatment including dates of receipt. In addition, accurate records will be kept regarding the date, lot number, and how much study treatment is dispensed and used by each subject in the study. Reasons for deviation from the expected dispensing regimen must also be recorded. At completion of the study, to satisfy regulatory requirements regarding drug accountability, all unused study treatment will be reconciled and destroyed according to applicable state, federal, and local regulations (any unused study drug will not be returned to lead site, but destroyed per local pharmacy SOPs).

8.2 Temodar/Temozolomide

Temodar contains temozolomide, an imidazotetrazine derivative. The chemical name of temozolomide is 3, 4-dihydro-3-methyl-4-oxoimidazo (5, 1-d) - as-tetrazine-8-carboxamide.

Each capsule for oral use contains either 5 mg, 20 mg, 100 mg, 140 mg, 180 mg, or 250 mg of temozolomide.

Only during Cycle 1, temozolomide should be taken orally at 150 mg/ m² Days 1-5 of a 28-day cycle. Thereafter, if absolute ANC $\geq 1.5 \times 10^9/L$ and platelet count $\geq 100 \times 10^9/L$, the dose should be escalated to 200 mg/m² Days 1-5 of a 28-day cycle.

Temozolomide is contraindicated in subjects who have a history of hypersensitivity reaction (such as urticarial, allergic reaction including anaphylaxis, toxic epidermal necrolysis, and Stevens-Johns syndrome) and subjects who have a history of hypersensitivity to dacarbazine.

8.2.1 Drug Interactions

Administration of valproic acid decreases oral clearance of temozolomide by about 5%.

8.2.2 Warnings and Precautions

- Myelosuppression (subjects treated with temozolomide may experience myelosuppression, including prolonged pancytopenia, which may result in aplastic anemia, which in some cases has resulted in a fatal outcome).
- Myelodysplastic syndrome (cases of myelodysplastic syndrome and secondary malignancies, including myeloid leukemia, have been observed)
- Pneumocystis pneumonia (there may be a higher occurrence of PCP when temozolomide is administered during a longer dosing regimen).
- Hepatotoxicity (fatal and severe hepatotoxicity have been reported in subjects receiving temozolomide).

8.2.3 Mechanism of Action/Absorption

Temozolomide is not directly active but undergoes rapid nonenzymatic conversion at physiologic pH to the reactive compound 5-(3-methyltriazen-1-yl)-imidazole-4-carboxamide (MTIC). The cytotoxicity of MTIC is thought to be primarily due to alkylation of DNA. Temozolomide is rapidly and completely absorbed after oral administration with a peak plasma concentration (C_{\max}) achieved in a median T_{\max} of 1 hour. Food reduces the rate and extent of temozolomide absorption. About 38% of the administered temozolomide total radioactive dose is recovered over 7 days: 37.7% in urine and 0.8% in feces.

8.2.4 Side Effects

The most common adverse reactions of Temozolomide ($\geq 10\%$ incidence) are: alopecia, fatigue, nausea, vomiting, headache, constipation, anorexia, convulsions, rash, hemiparesis, diarrhea, asthenia, fever, dizziness, coordination abnormal, viral infection, amnesia, insomnia, lymphopenia, thrombocytopenia, neutropenia, and leukopenia.

Please refer to the current Package Insert for a complete listing of all toxicities.

8.2.5 Availability & Supply

Temozolomide is commercially supplied and will not be provided by the study.

9.0 CORRELATIVES/SPECIAL STUDIES

Tolaney et al. published a translational study in which they evaluated whether cytokine levels in subjects enrolled in a phase II trial of cabozantinib for metastatic triple negative breast cancer. They measured levels of several cytokines at baseline, and every 3 weeks after starting cabozantinib therapy demonstrating that high levels of baseline sMET were associated with longer PFS. Furthermore, they showed that cabozantinib treatment was associated with changes in biomarker concentrations consistent with antivascular effects. Based on their preliminary data, we propose to measure sVEGFR2, PIGF, VEGF, HGF, sMET, VEGF-C, VEGF-D and soluble AXL in blood to verify the results collected by Tolaney et al.

In particular, we will determine if there is an earlier correlation that can be detected between levels of these cytokines, and PFR, as well as OS which may allow us to better predict treatment response early on in therapy.

9.1 Sample Collection Guidelines

Mandatory whole blood samples will be collected at Cycle 1 Day 1 before starting the treatment, at C2D15 (6 weeks), C4D1 (12 weeks), and at EOT. Approximately 20 ml of anticoagulated whole blood will be collected in 2 EDTA purple top tubes at each time point. Samples should be labeled with the corresponding subject's study ID number, initials, and date of collection. See the lab manual for more details, including shipping instructions.

10.0 STATISTICAL CONSIDERATIONS

10.1 Study Design/Study Endpoints

For Cohort 1, this is a single arm two-stage Simon design comparing 20% vs 39% 3-months PFS rate. If 3 or fewer out of first 14 subjects Cohort 1 are progression free at 3-months the trial will stop early. Otherwise, additional 28 more subjects will be enrolled to Cohort 1 in stage 2 (total sample size 42). At the end of the study a favorable outcome will be concluded if 13 or more subjects have documented PFS at 3 months. This is based on Simon two-stage optimal design, with $\alpha=0.05$, and $\beta=0.20$.

Exploratory group (Cohort 2): Up to 30 subjects with unresectable or metastatic soft tissue sarcoma (non-leiomyosarcoma) will be enrolled to obtain exploratory information for subjects with these histologies. If 3 or fewer out of first 14 subjects are progression-free at 3-months the final 16 subjects will not be enrolled. Cohort 2, will have the same first stage stopping rule (3 or fewer progression-free at 3 months), but due to the heterogeneity of disease, no formal hypothesis testing is planned if accrual is continued to a total of 30 patients. The first 14 subjects to be enrolled in the study in either cohort will serve as a safety lead in. After the first 14 subjects complete 1 cycle, investigators will review all grade 3 and 4 toxicities and confirm safety to proceed with additional subjects.

10.2 Sample Size and Accrual

Cohort 1: Minimum 14, Maximum 42.

Cohort 2: Minimum 14, Maximum 30.

Accrual is expected to take 2 years (~ 3 per month across multiple centers).

10.3 Data Analyses Plans

PFS and OS will be estimated using Kaplan-Meier methods for Cohort I and II.

The percent progression-free at 3 months will be summarized in terms of these point estimates, along with a 95% confidence interval. Toxicities will be tabulated and summarized by the number of subjects experiencing each toxicity.

No formal hypothesis test is planned for Cohort 2.

The first 14 subjects will serve as a safety lead in and will be comprised of subjects that enroll in both Cohort 1 and Cohort 2. During the safety lead-in, any grade 5 possibly related event in this first 3 months will hold accrual pending review by the DSMC/IRB. In addition, if 2 of the first 6, or subsequently more than 30% have to stop therapy in the first cycle, the study will be put on hold pending review by the DSMC/IRB. The DSMC will also receive a report after the 14th subject is enrolled and treated for at least one cycle, to review drug-related AEs and ensure the safety to continue enrollment.

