1.3 Rationale for the Current Study

There are several reasons to consider the combination of temozolomide and cabozantinib in STS. There is prior evidence that temozolomide, and cabozantinib individually have clinical benefit in patients with STS.^{31,35} The targets of both agents are relevant in metastatic STS, with cabozantinib acting specifically on VEGFR2, and MET, and temozolomide mediating action through alkylation. The utilization of cabozantinib in combination with oral temozolomide is anticipated to produce a synergistic anti-tumor effect, and is worthwhile to explore in patients with STS. The desired effect of palliative chemotherapy is tumor shrinkage, and delay in progression in such a way that improves the wellbeing, and activity of patients.

A dose of 40 mg PO daily of cabozantinib combined with a dose of 150 mg/m² PO Days 1-5 of temozolomide (Cycle 1), the escalated to 200 mg/m² PO Days 1-5, based on absolute neutrophil and platelet counts, was chosen for this study. The dose outlined above for temozolomide during Cycle 1 was modified due to observed toxicity. For Cycles 2+, the dose is standard and has received FDA approval at the proposed dose and route of administration. The cabozantinib dose chosen for this study has previously been demonstrated to have a tolerable toxicity profile in a cabozantinib and temozolomide combination treatment in a phase I dose escalation study.⁴⁰ Results from this study reported that 40mg daily cabozantinib was found to be the MTD in combination treatment with temozolomide plus radiotherapy or after radiotherapy in patients with high-grade gliomas and was well tolerated in patients.⁴⁰

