4.2 Treatment Plan

Subjects will be registered to 2 cohorts based on disease. Subjects with unresectable or metastatic uterine and non-uterine leiomyosarcoma will be registered to cohort 1 and subjects with unresectable or metastatic other soft tissue sarcomas (non-leiomyosarcoma) will be registered to cohort 2. The first 14 subjects to be enrolled in the study in either cohort will serve as a safety lead in. After the first 14 subjects complete 1 cycle, investigators will review all grade 3 and 4 toxicities and confirm safety to proceed with additional subjects. These subjects will be observed for 2 weeks following completion of cycle 1. Refer to Section 4.4 for details. A Simon stage II design will be employed in cohort 1 to determine favorable outcome. Cohort 2 is considered exploratory.

Subjects will take oral cabozantinib (40 mg starting dose) once daily for 28 days and temozolomide 150 mg/m² (Cycle 1) on Days 1-5 of each 28 day cycle. For

Cycles 2+, temozolomide should be escalated to 200 mg/m² on Days 1-5 of each 28 day cycle, if absolute ANC $\geq 1.5 \times 10^9/L$ and platelet count $\geq 100 \times 10^9/L$.

Treatment will continue until either disease progression, the occurrence of unacceptable drug-related toxicity or for other reason(s) for subject withdrawal as described in [Section 4.8](#). Subjects who are removed from the study treatment for toxicity should be followed until toxicity resolves to Grade 1 or baseline.

Subjects should be instructed to immediately inform the treating investigator of any AEs. Subjects experiencing dizziness, sleepiness, or other symptoms that could influence alertness or coordination should be advised not to drive or operate other heavy machinery.

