40. Schiff, D., et al., Phase 1 dose escalation trial of the safety and pharmacokinetics of cabozantinib concurrent with temozolomide and radiotherapy or temozolomide after radiotherapy in newly diagnosed patients with high-grade gliomas. *Cancer*, 2016. 122(4): p. 582-7.
doi:10.1097/CAD.000000000000108

APPENDIX A - DOSE MODIFICATION ALGORITHMS FOR POTENTIAL COMBINATION TREATMENT RELATED ADVERSE EVENTS

AE Terms & Descriptions	Dose Modification Algorithms
Diarrhea	
a. Grade 1-2 (duration < 48 hr)	a. Continue Cabozantinib at the current dose. If it does not improve with supportive measures consider a dose reduction. Continue temozolomide at the current dose.
b. Intolerable Grade 2 or Grade 3	b. Interrupt Cabozantinib and temozolomide until Grade ≤ 1 then consider restarting Cabozantinib at reduced dose. Dose reduce temozolomide by one dose level for Grade 3 only. Discontinue temozolomide for grade 4.
	c. Refer to the Table 0-3 for the management of diarrhea.
Neutropenia	
a. Neutrophil count <1.5	a. Interrupt temozolomide and cabozantinib until neutrophil count $\geq 1.5 \times 10^9/L$.
b. Neutrophil count <1.0	b. Interrupt temozolomide and cabozantinib until $\geq 1.5 \times 10^9/L$. Reduce temozolomide by 1 dose level. Continue cabozantinib at the same.
c. Neutrophil count <0.5	c. Discontinue temozolomide, interrupt cabozantinib until neutrophil count is $\geq 1.5 \times 10^9/L$ then resume at same dose.
Febrile Neutropenia	
Grade 3 or 4	Interrupt temozolomide and cabozantinib until resolved. Upon resumption, reduce temozolomide by 1 dose level. Continue cabozantinib at the same dose.
Thrombocytopenia	
Grade 1 or 2	Interrupt temozolomide until $\geq 100 \times 10^9/L$. Continue cabozantinib.

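### The only numeric hold rule for non-fatal toxicity counts Cycle 1 stops, before the planned, count-conditional one-third temozolomide escalation in Cycle 2

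*Combined protocol and SAP*

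**What the plan says.** Section 10.3 and the Study Summary set two accrual holds. The first concerns discontinuation: the study is held "if 2 of the first 6, or subsequently more than 30% have to stop therapy in the first cycle". The second concerns deaths: "During the safety lead-in, any grade 5 possibly related event in this first 3 months will hold accrual". Either one leads to DSMC/IRB review.

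Sections 4.2, 4.3 and 8.2 set the dosing. Subjects take "temozolomide 150 mg/m² (Cycle 1) on Days 1-5 of each 28 day cycle", then 200 mg/m² from Cycle 2 if ANC is at least 1.5 × 10⁹/L and platelets are at least 100 × 10⁹/L. Section 1.3 adds: "The dose outlined above for temozolomide during Cycle 1 was modified due to observed toxicity".

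Other lead-in safeguards are:

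- **Section 4.2 (also 10.1):** "After the first 14 subjects complete 1 cycle, investigators will review all grade 3 and 4 toxicities", and confirm that it is safe to go on.
- **Section 4.4:** accrual is interrupted after 14 subjects, who are watched for at least 2 weeks beyond Cycle 1. A subject who leaves for a non-toxicity reason before completing a 4-week observation period is replaced.
- **Section 10.3:** the DSMC receives a report on drug-related AEs once the 14th subject has had at least one cycle.
- **Sections 14.3 and 14.6:** the Protocol Management Team and the DSMC monitor toxicity throughout.

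For an ANC below 0.5, Appendix A reads "Discontinue temozolomide, interrupt cabozantinib until neutrophil count is" at least 1.5 × 10⁹/L, after which cabozantinib resumes at the same dose.

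**The concern.** Section 4.4 says that experience with this combination is limited and that the lead-in is there to rule out prohibitive toxicity. The one rule that puts a number on non-fatal toxicity closes its window as the planned temozolomide dose goes up. A subject who tolerates Cycle 1 and must stop for toxicity in Cycle 2 counts as no stop. A run of such subjects would not trip the rule, and any decision to pause would rest on judgement.

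Two gaps in wording add to this. First, the plan does not define stopping therapy when there are two drugs. Under Appendix A a subject can permanently lose temozolomide and continue cabozantinib, and the plan does not say whether that counts. Second, the related-death hold is tied to the lead-in, so up to 72 − 14 = 58 subjects fall outside it.

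**Working it through.** **Plan's own figure.** The plan gives no operating characteristics and no acceptable stop rate for the hold rule, so there is nothing to reproduce. Its stated error rates (α = 0.05, β = 0.20) belong to the Cohort 1 efficacy design and do not enter here.

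**Inputs from the documents.** Thresholds are 2 of the first 6, then more than 30%, with a Cycle 1 window (10.3). The lead-in has 14 subjects (10.3). Temozolomide is 150 then 200 mg/m² (4.2). Accrual is about 3 per month (10.2).

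**Assumed inputs.** Stop rates; independent subjects assessed in enrollment order; the rule checked after each subject and followed to subject 14.

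**1. Dose step.** 200/150 − 1 = 0.33.

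**2. Hold boundary.** Up to subject 6, hold at 2 stops. After that, hold when the count exceeds 0.30 × m among m subjects: 3 stops at m = 7 to 9, 4 at m = 10 to 13, 5 at m = 14.

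**3. Hold probability.** The first-six part is 1 − (1 − p)⁶ − 6p(1 − p)⁵. At p = 0.10 this is 1 − 0.531 − 0.354 = 0.114. Carrying the exact binomial forward from subject 7 to 14 adds the later crossings:

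| True stop rate p in the counted window | First six | Through subject 14 |
|---|---|---|
| 5% | 0.033 | 0.035 |
| 10% | 0.114 | 0.131 |
| 20% | 0.345 | 0.428 |
| 25% | 0.466 | 0.582 |
| 30% | 0.580 | 0.716 |

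**4. Effect of the window.** Fix Cycle 1 stops at 10%. Cycle 2 stops do not enter the present rule, so its hold probability stays at 0.13. With the same thresholds over Cycles 1 and 2:

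| Cycle 1 + Cycle 2 (share of all subjects) | Total | Present rule | Both cycles counted |
|---|---|---|---|
| 10% + 10% | 20% | 0.13 | 0.43 |
| 10% + 15% | 25% | 0.13 | 0.58 |
| 10% + 20% | 30% | 0.13 | 0.72 |

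A lower Cycle 1 rate shows the same pattern. With 5% stopping in Cycle 1 and 20% of the remainder in Cycle 2, the total is 1 − 0.95 × 0.80 = 24%, and the probabilities are 0.035 and 0.55.

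**5. What the death rule can see.** The chance of at least one possibly related death in 14 subjects is 1 − (1 − q)¹⁴. At assumed 3-month risks q of 1%, 2% and 5% this is 0.13, 0.25 and 0.51. Its window reaches past the escalation, but it does not respond to non-fatal toxicity.

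**6. What the reviews can see.** At 3 per month, evenly spaced (one every 10 days, assumed), subject 14 starts on day 130 and ends Cycle 1 on day 158. Subject i is then 158 − 10(i − 1) days from first dose. This is at least 56 days for i up to 11, so 11 of 14 subjects would have 8 weeks of follow-up. After the further 2 weeks (day 172) it is 12 of 14.

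**The case against.** A reader might infer that the Cycle 1 rule is the trial's only toxicity rule and that the escalated regimen is never examined. The documents do not support that. The related-death hold runs for 3 months and so covers Cycles 2 and 3. If Cycle 2 starts on time, the 2 weeks of observation after Cycle 1 include the whole first course at the higher dose. Neither the investigator review nor the DSMC report is limited to Cycle 1 events, and by step 6 most lead-in subjects could already contribute Cycle 2 data. The 58 later subjects are outside the automatic death hold, but DSMC and team monitoring and expedited SAE reporting (7.4) still cover them.

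Nor does Section 1.3 show that the higher dose is unsafe. Its next sentence describes the Cycles 2+ dose as standard and FDA-approved. Escalation depends on counts, and the plan gives no figure for how many subjects will receive it.

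The calculation has limits too. The stop rates are assumed, and fixed thresholds over a window twice as long raise the hold probability mechanically: 10% in each cycle takes it from 0.13 to 0.43. Without a stated acceptable rate, the numbers cannot show that the extra holds would be the right ones.

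All of this stands. It leaves the narrower point intact: none of the other safeguards gives a numeric trigger for non-fatal toxicity after escalation. The word "subsequently" in the rule may or may not extend the 30% limit beyond subject 14. On either reading only first-cycle stops count.

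**Conclusion.** The point holds in its narrow form. The rule's window and the dosing schedule do not match, and the plan should reconcile them. At the planned higher dose, protection against non-fatal toxicity rests on reviews without thresholds.

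As an illustration of size, with 10% stopping in Cycle 1 the hold probability within the lead-in is 0.13 whatever happens in Cycle 2, against 0.43 to 0.72 if both cycles counted at totals of 20% to 30%. The blindness to Cycle 2 follows from the text alone. The probabilities rest on assumed rates, independence and a stop at subject 14. The change is worth making, but the point does not show that the lead-in fails or that the regimen is unsafe.

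**What to change.** Make these changes consistently in the Study Summary and Sections 4.2, 4.4, 10.1 and 10.3. Section 4.4 must be included because it holds the 4-week observation period, the replacement rule and the accrual interruption; left as it is, it would contradict the new window.

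1. Count stops for related toxicity through the end of Cycle 2.
2. Time the 14-subject review and DSMC report to when the 14th subject completes Cycle 2 or stops earlier.
3. State that permanent discontinuation of either drug for related toxicity counts as a stop.
4. State whether subjects who leave for progression before the end of Cycle 2 stay in the denominator or are replaced. A scan falls at C2D15, and the null 3-month progression-free rate is only 20%, so such exits are likely.
5. Apply the hold for possibly related Grade 5 events to every enrolled subject.
6. Have the sponsor confirm that 2 of 6 and 30% suit the longer window, and report the hold probabilities for the thresholds chosen.

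**Cost.** The pause, measured from the 14th subject's first dose, goes from at least 42 days (28 + 14) to 56, about two weeks more. With unchanged thresholds a hold becomes clearly more likely, as step 4 shows. A hold leads to DSMC/IRB review and not termination. No dose or patient-level treatment rule is proposed.
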